16.2.2.1. Analysis of the Primary Endpoint

Counts and change from Baseline in counts for each of the lymphocyte subsets will be descriptively summarized at each applicable visit. Furthermore, the primary endpoints will be summarized in various ALC subgroups to evaluate the nature of change in each subset in relation to the change in ALC. Additionally, a mixed model for repeated measures (MMRM) will be used, which will be fit with the change from Baseline for each of the lymphocyte subsets as the dependent variable and will include ALC subgroups, visit, corresponding Baseline counts, age, gender, and ALC groups-by-visit interaction as fixed effects to estimate the difference between ALC subgroups. Point estimates and 2-sided 90% confidence intervals (CIs) will be derived from the model. Appropriate transformation may be performed based on the distribution of data.

[figure not shown]
ALC subgroups of interest include (1) subjects who have all ALC values \geq LLN up to Week 48, (2) subjects who have at least 1 ALC value $<$ LLN over 48 weeks, and (3) subjects who have at least 2 ALC values $<$ LLN over 48 weeks. Additional subgroups will be further defined in the Statistical Analysis Plan.

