5.3.1 Analysis of the Primary Endpoint

The primary endpoints are the changes in lymphocyte subset counts for up to 48 weeks. The actual value, change and percent change from baseline in count and percent for each lymphocyte subset will be descriptively summarized at each applicable visit. Graphical display of median (Q1-25 percentile/Q3-75 percentile) of actual value and percent change from baseline in count and percent for each lymphocyte subset over time will also be presented. The Wilcoxon signed rank test will be used to test if the change and percent change from baseline in count and percent for each lymphocyte subset is different from zero. Listings of lymphocyte subsets will also be presented.

Furthermore, the primary endpoints will be summarized in various ALC subgroups to evaluate the nature of change in each subset in relation to the change in ALC.

ALC subgroups of interest include (1) subjects who have all ALC values \geq LLN ($0.91 \times 10^9/L$) up to Week 48, and (2) subjects who have at least 1 ALC value $<$ LLN over 48 weeks. A mixed model for repeated measures (MMRM) will be used to estimate the difference between ALC subgroups at each post-baseline visit up to Week 48. The model will be fitted with the change from baseline in count up to Week 48 for each of the TBNK lymphocyte subset as the dependent variable and will include ALC subgroup (all ALC values

CONFIDENTIAL

The information contained herein may not be used, disclosed, or published without the written consent of Biogen Idec MA Inc.

	Protocol 109MS310 An Open-Label Study to Assess the Effects of BG00012 on Lymphocyte Subsets in Subjects With RRMS	Final Version 1.0
---	---	--------------------------

\geq LLN up to Week 48; at least 1 ALC value $<$ LLN over 48 weeks), visit, corresponding Baseline counts, age, gender, and ALC subgroup-by-visit interaction as fixed effects. An unstructured variance-covariance matrix structure will be used in the MMRM model. Least squares (LS) mean, standard error, LS mean difference, 2-sided 95% confidence intervals (CIs) and p-values will be reported. Before the MMRM analysis, appropriate transformation may be performed based on the distribution of each TBNK lymphocyte subset parameter. The same analysis may be applied to other subsets.

Additional subgroups based on ALC values over time are defined:

- 1) ALC $< 0.5 \times 10^9/L$ for ≥ 6 months (24 weeks);

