5.3.2 Analysis of the Secondary Endpoints

The secondary endpoints are the changes from baseline in Ig isotypes (including IgA, IgM, IgG and IgG subclasses) and ALCs for up to 48 weeks. The actual values, change and percent change from baseline for Ig isotypes and ALCs at each applicable visit will be descriptively summarized. Graphical display of mean (+/- SE) of actual values and percent change from baseline over time in Ig isotypes will be presented as well. Individual patient's Ig isotypes will also be listed.

In addition, MMRM analysis will be conducted for each Ig isotype and for ALC with the change from baseline up to Week 96 as the dependent variable. The model will include visit, corresponding baseline value, age, and gender as fixed effects and an unstructured variance-covariance matrix structure. LS mean, standard error and 95% CIs will be reported for each visit.

CONFIDENTIAL

The information contained herein may not be used, disclosed, or published without the written consent of Biogen Idec MA Inc.

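### The ALC-subgroup MMRM fits one baseline slope to all visits, which is likely to overstate the subgroup difference at Week 4 and understate it at Week 48

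*SAP*

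**What the plan says.** SAP 5.3.1 states that the MMRM "will be used to estimate the difference between ALC subgroups at each post-baseline visit up to Week 48". The outcome is on the count scale: "The model will be fitted with the change from baseline in count up to Week 48". Apart from ALC subgroup, the fixed effects are "visit, corresponding Baseline counts, age, gender, and ALC subgroup-by-visit interaction as fixed effects". On covariance and scale it adds "An unstructured variance-covariance matrix structure will be used in the MMRM model" and, before the analysis, "appropriate transformation may be performed based on the distribution of each TBNK lymphocyte subset parameter".

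Protocol 16.2.2.1 describes the same mean model: "corresponding Baseline counts, age, gender, and ALC groups-by-visit interaction as fixed effects to estimate the difference between ALC subgroups".

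In both documents subgroup is crossed with visit and baseline is not. Neither gives a sensitivity model with a baseline-by-visit term. Neither reports or projects baseline counts by subgroup.

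**The concern.** The model targets a separate subgroup difference at each of six visits but adjusts every one of them with the same baseline slope. In a randomised comparison this would matter little, because baseline means agree in expectation. Here the groups are formed by what ALC does after treatment starts, so a baseline gap does not average out. Wherever the slope at a visit differs from the common slope, the mismatch multiplied by the baseline gap goes into the subgroup difference at that visit. The unstructured covariance describes the residuals and does not repair the mean model.

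At stake is the time course of the contrast, and Week 48 in particular. The sample size section illustrates precision at Week 48, and SAP 5.3.1 reports 95% confidence intervals and p-values from this model.

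**Working it through.** **1. The plan's own figures.** SAP 4 and Protocol 16.7 give 180 evaluable subjects, 76% and 24% by subgroup, and 10% discontinuation. 180/0.90 = 200. 180 × 0.76 = 136.8 and 180 × 0.24 = 43.2, so 137 and 43. For CD4 (log SD 0.32, ratio 0.8), the standard error is 0.32 × √(1/137 + 1/43) = 0.056. The 90% CI is 0.8 × exp(±1.645 × 0.056) = 0.730 to 0.877, against 0.73 to 0.88 in the table. These reproduce, and none of them depends on this point.

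**2. The bias formula.** At visit t:

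bias = (b_t − b_common) × (baseline mean, low-ALC group − baseline mean, normal-ALC group)

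Here b_t is the within-subgroup slope of change on baseline at visit t, and b_common is the slope the model fits to all visits. The reference is the same model with visit-specific slopes. The bias is exactly zero if the slopes are equal across visits or if the baseline means are equal.

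**3. Are both conditions plausible from the documents?**
- *Baseline gap.* SAP 5.3.1 sets LLN at 0.91 × 10⁹/L. Protocol 8.2 excludes only a confirmed screening ALC at or below LLN. Protocol 5.3.2 reports a mean fall of about 30%. A subject with that average fall crosses LLN if baseline ALC is below 0.91/0.70 = 1.3. Low starters should therefore be over-represented in the low group. T, B and NK counts are components of ALC and should follow.
- *Changing slope.* Protocol 5.3.2 describes a gradual decline over the first year. If loss is roughly proportional to baseline, the slope of raw change on baseline steepens as the loss grows.

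**4. A bound without simulation.** Assume a Week 48 slope of −0.30 (proportional loss), a common slope of −0.10 to −0.20, and a gap of 100 to 250 cells/mm³.
- Smallest: (−0.30 + 0.20) × (−100) = +10 cells.
- Largest: (−0.30 + 0.10) × (−250) = +50 cells.

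Both move the Week 48 estimate toward no difference.

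**5. Simulation, base scenario, CD4.** All inputs beyond the 30% fall are assumptions: baseline ALC median 1.85–2.0 × 10⁹/L, between-subject log SD 0.24–0.28, log-decline SD 0.20–0.36, measurement log SD 0.12–0.13, CD4 fraction 0.45. Data are complete; age and gender are omitted. Large-sample values use 200,000 subjects; values at N = 180 use 400 trials.

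On raw counts, baseline means are 965 and 713 cells/mm³. Slopes run from −0.242 (Week 4) to −0.506 (Week 48), and the common slope is −0.311. It sits near the early slopes because Weeks 4, 8 and 12 carry 0.33 + 0.29 + 0.24 = 0.86 of the weight.
- Week 48: (−0.506 + 0.311) × (713 − 965) = +49 cells; simulated difference −197 instead of −246.
- Week 4: (−0.242 + 0.311) × (713 − 965) = −17 cells; simulated difference −95 instead of −77.

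On the log scale, slopes run from −0.217 to −0.380 and the common slope is −0.239. Taking the ALC gap ln(1.51/2.03) = −0.296 as the CD4 gap, the Week 48 bias is (−0.380 + 0.239) × (−0.296) = +0.042. The ratio becomes 0.646 instead of 0.619.

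**6. Four scenarios.** Percentages are changes in the size of the subgroup difference. SE columns are mean bias over mean standard error at N = 180.

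| Scenario | Below LLN | Raw, Week 4 / Week 48 | Raw Week 48 bias/SE | Log, Week 4 / Week 48 | Log Week 48 bias/SE |
|---|---|---|---|---|---|
| Base | 21.7% | +22.4% / −19.9% | 45.9/42.3 = 1.09 | +6.8% / −8.7% | 0.037/0.053 = 0.70 |
| Smaller spread of decline | 20.7% | +44.9% / −29.5% | 45.6/34.5 = 1.32 | +10.0% / −10.8% | 0.033/0.047 = 0.70 |
| Larger spread of decline | 20.8% | +9.5% / −13.2% | 43.4/54.4 = 0.80 | +3.1% / −6.1% | 0.033/0.062 = 0.53 |
| Earlier decline | 24.4% | +17.1% / −16.7% | 42.5/40.3 = 1.05 | +5.9% / −7.8% | 0.038/0.051 = 0.75 |

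Week 48 coverage of the 95% CI under the common slope is 80–94% (raw) and 90–92% (log). With the interaction it is 99–100% (raw, so conservative) and 96–98% (log).

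**7. Other assumed inputs.** With baseline ALC median 1.9, log SD 0.28 and within-subject log SD 0.10–0.20, raw Week 48 shrinkage fell as low as 8% (0.5 SE). On the log scale no run exceeded 0.9 SE. The direction did not change. Log-scale runs for other subsets gave 4.6% (0.31 SE) for a B-cell-like and 3.6% (0.22 SE) for an NK-like parameter.

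**The case against.** **The baseline gap is inferred.** A reader might take it that the documents show the subgroups starting at different counts, and so that the model is biased as a matter of record. They show neither. No baseline ALC or subset count by subgroup appears, and the baseline distribution used above is assumed. This stands, and it limits the claim to a likely bias.

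**The planning scale is log.** The sample size table uses ratios and a log-scale SD, and SAP 5.3.1 permits a transformation. A uniform proportional fall does not steepen the log-scale slope; what remains there comes from sorting subjects on their later ALC. This stands in part. The effect drops to 6–11% for CD4 but does not vanish, and the transformation is optional, so raw counts remain the default.

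**The study is descriptive.** Protocol 16.2.2 plans no hypothesis test, and by-visit summaries by ALC subgroup do not use the common slope. True, but those summaries are not adjusted for baseline, and the SAP does attach p-values to the MMRM contrast.

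**Two extensions look tempting and fail.**
- SAP 5.3.2 also lacks the interaction: "The model will include visit, corresponding baseline value, age, and gender as fixed effects and an unstructured variance-covariance matrix structure". That model has no subgroup contrast. With complete data, its LS means at the overall mean baseline are the same with or without the term. A single-group simulation at n = 180 agreed to six decimals, with standard errors within 2%. Only dropout related to baseline could separate the two models, and nothing here demonstrates that.
- SAP Appendix 1 lists granulocytes and monocytes among the TBNK parameters. Neither a baseline gap nor a steepening slope follows for these, so the argument does not cover them.

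**Conclusion.** The omission is clear in both documents, and both conditions for bias are likely given how the subgroups are formed and how counts are expected to fall. The common slope is then likely to overstate the CD4 subgroup difference at Week 4 and understate it at Week 48. Illustrative Week 48 shrinkage is roughly 8–30% on raw counts (0.5 to 1.3 SE at N = 180) and roughly 6–11% on the log scale (under one SE). Effects should be smaller for other lymphocyte subsets.

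The direction rests on a lower baseline in the low-ALC group and a slope that steepens with time. The percentages rest on assumed distributions and complete data. No sample size or error rate depends on the point. It merits a change because the bias falls on the quantity the model exists to estimate and the remedy is cheap. Confidence in the size is moderate.

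**What to change.** In SAP 5.3.1 and Protocol 16.2.2.1, add the interaction of baseline count with visit to the ALC-subgroup MMRM. Report baseline counts of each subset by ALC subgroup, so that a reader can see whether the gap exists and how large it is.

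The cost is one term in the model statement, 6 − 1 = 5 degrees of freedom for six visits, plus one descriptive table. Data collection and sample size do not change. This argument calls for no change to SAP 5.3.2. The added term does not remove the separate problem that the subgroups are defined by post-baseline ALC, of which the lymphocyte subsets are components.

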10. DISCONTINUATION OF STUDY TREATMENT AND/OR WITHDRAWAL OF SUBJECTS FROM THE STUDY

10.1. Discontinuation of Study Treatment

A subject *must* permanently discontinue study treatment for any of the following reasons:

- The subject becomes pregnant. Study treatment must be discontinued immediately. Report the pregnancy according to the instructions in Section 15.4.1.
- The subject withdraws consent to continue study treatment.
- The subject experiences a medical emergency that necessitates permanent discontinuation of study treatment.
- The subject is unable to tolerate study treatment at 240 mg BID (see Section 11.2.4).
- The subject receives any concomitant medications not allowed by the protocol.
- The subject experiences any of the laboratory abnormalities requiring permanent discontinuation of treatment defined in [Table 3](#).
- The subject experiences more than 1 deviation of the same laboratory parameter that meets the threshold limits defined in [Table 3](#) at any time during the study.
- The subject experiences more than 2 different deviations of laboratory parameters that meet the threshold limits defined in [Table 3](#) at any time during the study. On a third occasion, the subject is required to discontinue dosing for the remainder of the study.
- If a subject has a lymphocyte count $<500/\text{mm}^3$ persisting for more than 24 weeks consecutively, study treatment must be temporarily withheld. Study treatment may be resumed after lymphocyte counts recover $>\text{LLN}$ on 2 consecutive occasions at least 4 weeks apart. If the subject develops a lymphocyte count $<500/\text{mm}^3$ on 1 occasion (confirmed by repeat testing) on resumption of study treatment, the subject must permanently discontinue study treatment and will continue protocol-required visits and assessments (see Section 11.3).
- If a subject's lymphocyte count remains $<\text{LLN}$ for 24 weeks consecutively after study treatment has been temporarily withheld due to lymphocyte count $<500/\text{mm}^3$ for more than 24 weeks, the subject must permanently discontinue study treatment.
- At the discretion of the Investigator for medical reasons or for noncompliance.

The reason for discontinuation of study treatment must be recorded in the subject's case report form (CRF).

Subjects who discontinue treatment may remain in the study and continue protocol-required tests and assessments.

CONFIDENTIAL

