2 STUDY DESIGN

2.1 Study Overview

This is an open-label, multicenter study to evaluate the effects of BG00012 on lymphocyte subtypes and Ig isotypes. Approximately 200 subjects were treated in approximately 100 sites in North America and Europe.

After the Screening Visit (up to 28 days) if required per local guidelines and if not already available within the previous 3 months, a magnetic resonance imaging (MRI) scan should be performed locally before starting therapy with BG00012 as per local guidelines. Subjects will then receive BG00012 treatment for 96 weeks (Treatment Period). Blood samples for lymphocyte subset analysis, as well as blood samples for the determination of each subject's complete blood count with differential, will be collected at Screening, Baseline (Day 1), and Weeks 4, 8, 12, 24, 36, 48, 60 (complete blood count [CBC only]), 72, 84 (CBC only), and 96. Clinical samples for the analysis of blood chemistries will be collected at Screening, Baseline (Day 1), and Weeks 4, 8, 24, 48, and 96. A post-treatment follow-up visit, at which safety assessments will be performed, will occur 4 weeks after the final dose of BG00012.

Subjects who temporarily withhold or permanently discontinue study treatment for any other reason than lymphopenia and have a lymphocyte count <LLN will continue protocol-required visits and assessments and will also be followed every 4 weeks for 24 weeks, then every 12 weeks (unless clinically indicated more often or at the Investigator's discretion) until the lymphocyte count is \geq LLN or for up to 48 weeks following drug discontinuation, whichever occurs sooner.

Subjects who develop a confirmed lymphocyte count of <500 cells/mm³ at any time during the study will be monitored every 4 weeks. If the lymphocyte count stays <500 cells/mm³ for 24 weeks, the subject will temporarily withhold study treatment. If the lymphocyte count does not recover to LLN within 24 weeks while study treatment is temporarily withheld, study treatment will be discontinued permanently.

CONFIDENTIAL

The information contained herein may not be used, disclosed, or published without the written consent of Biogen Idec MA Inc.

	
Protocol 109MS310 An Open-Label Study to Assess the Effects of BG00012 on Lymphocyte Subsets in Subjects With RRMS
	Final Version 1.0
---	---	--------------------------

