5 STATISTICAL ANALYSIS METHODS

5.1 General consideration

The statistical software, SAS[®], will be used for all summaries and statistical analyses.

This study only includes a single arm. In general, statistical analyses will be descriptive in nature with appropriate measures of variation provided where applicable. For continuous endpoints, number of subjects in the analysis population, number of subjects with non-missing observations, mean, standard deviation (SD), median, minimum and maximum will be reported. For categorical endpoints, number of subjects in the analysis population, number with non-missing observations, and the percent of those with data in each category will be summarized.

Several analysis populations are defined for different analysis purposes in this study. An overview of these analysis populations will be summarized.

- Pharmacodynamic Population - it is defined as all subjects who receive at least 1 dose of study treatment and have at least 1 pharmacodynamic measurement after Baseline.

CONFIDENTIAL

The information contained herein may not be used, disclosed, or published without the written consent of Biogen Idec MA Inc.

	Protocol 109MS310 An Open-Label Study to Assess the Effects of BG00012 on Lymphocyte Subsets in Subjects With RRMS	Final Version 1.0
---	---	--------------------------

- Safety Population – it is defined as all subjects who receive at least 1 dose of study treatment.

- [REDACTED]

[REDACTED]

In general, for data that are summarized by visit, any early withdrawal, unscheduled or scheduled visits will be assigned to an appropriate scheduled visit by using a mid-point of the two visits windowing scheme. The date of first dose will be the reference point. The detailed windowing rules for lymphocyte subsets, hematology, blood chemistry and vital signs are available in [Appendix 2](#). After windowing, if there is only 1 record in the visit window, then this record will be selected; if there are multiple records falling into the same visit window with different distance from the target day then select the one closest to the target day; if there are 2 visits with the same distance from the target day, but one is before the target day and the other is after the target day, then select the later one; for laboratory test, if more than one observation falls in the same distance from the target regular scheduled visit day, the mean observation will be calculated and used in the summary statistics and analyses.

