- 2) $0.5 \times 10^9/L \leq ALC < 0.8 \times 10^9/L$ for ≥ 6 months (excluding $< 0.5 \times 10^9/L$ for ≥ 6 months);
- 3) $<$ LLN any time (excluding $< 0.8 \times 10^9/L$ for ≥ 6 months);
- 4) ALC always \geq LLN.

Summary of actual value, change and percent change from baseline in count and percent for each lymphocyte subset will be presented by the ALC subgroups defined above.

The following subgroups analyses based on ALC during the first 48 weeks will be performed:

- 1) At least 2 ALC values $<$ LLN in the first 48 weeks;
- 2) Always \geq LLN or with one ALC $<$ LLN in the first 48 weeks

Additionally subgroups analyses based on baseline ALC quartiles will also be explored. The same descriptive summary on these subgroups will be applied to the count and percent for the TBNK lymphocyte subsets and may be applied to other subsets. Additional subgroups of interest may also be explored.

The correlation between TBNK actual value and ALC will be summarized by visit and also presented as plots.

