- The incidence of treatment-emergent AEs that led to dose reduction will be presented by SOC and PT.

SAEs and severe AEs

- The incidence of treatment-emergent SAEs will be presented by SOC and PT. Individual SAEs will be listed. The information presented will include subject ID, treatment, SOC and PT, date of onset, severity, and relationship to and action taken with the study drug.
- The incidence of treatment-emergent severe AEs classified by SOC and PT will be summarized.

Infections

The incidence of treatment-emergent infections, serious infections, and potential opportunistic infections by system organ class and preferred term will be summarized by subgroups based on the ALC values over time.

PML

Given that PML has been observed very rarely in patients who receive BG00012, any PML cases in this study will be listed.

Pancreatitis

Listing of events associated to pancreatitis will be presented.

Death

Death is classified as an outcome, not as an AE. Therefore, cause of death will be listed as the AE. Death will only be listed as an AE when the cause of death is unknown (e.g., in the case of sudden death). . The information presented will include subject ID, treatment group, SOC and PT, date of death, cause of death, and relationship to the study drug.

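### The four ALC-over-time subgroups are not exhaustive: a spell below 0.8 × 10⁹/L of 24 weeks or more that crosses 0.5 can fit no group

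*SAP*

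**What the plan says.** SAP 5.3.1 introduces the grouping with "Additional subgroups based on ALC values over time are defined" and lists four groups (units × 10⁹/L; LLN = 0.91):

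1. "ALC $< 0.5 \times 10^9/L$ for" at least 6 months (24 weeks).
2. "0.5 \times 10^9/L \leq ALC < 0.8 \times 10^9/L$ for" at least 6 months, leaving out those below 0.5 for at least 6 months.
3. Any count below the LLN, with an exclusion: "LLN any time (excluding $< 0.8 \times 10^9/L$ for" at least 6 months).
4. ALC always at or above the LLN.

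Actual value, change and percent change of each lymphocyte subset are tabulated by these groups. SAP 5.4.1 says that infections, serious infections and potential opportunistic infections "will be summarized by subgroups based on the ALC values over time". It cites no section number, but only the 5.3.1 grouping carries that label.

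SAP 5.3.1 does not say whether the 6 months must be unbroken, how time between visits is counted, or which ALC values are used. The windowing rule in SAP 5.1 is limited: "for data that are summarized by visit, any early withdrawal, unscheduled or scheduled visits will be assigned to an appropriate scheduled visit". Protocol 10.1, by contrast, specifies an unbroken period where it needs one: "persisting for more than 24 weeks consecutively".

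**The concern.** Group 3 removes everyone with at least 6 months below 0.8. Groups 1 and 2 take back only those who spent at least 6 months inside a single band. A spell below 0.8 that crosses 0.5 can be long enough to trigger the exclusion yet too short in each band to qualify for group 1 or 2.

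The pattern is realistic. Table 4 in Protocol 11.3.1 has an instruction for counts intermittently below 500/mm³ for more than 24 weeks. Under SAP 2.1, subjects with a confirmed count below 500 "at any time during the study will be monitored every 4 weeks", so such series will be recorded.

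The subjects affected have prolonged low counts, the setting in which Protocol 5.3.2 reports PML. Read literally, the rule drops them from the split subset and infection tables. If a programmer instead reads group 3 as everyone below the LLN who is not in group 1 or 2, they join the mildest lymphopenic group despite 24 weeks or more below 0.8. The two readings give different tables, and the choice could be made after the data are seen.

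**Working it through.** There is no stated figure to reproduce; the question is whether the four definitions cover every subject.

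**Duration readings.** Time can be consecutive (longest unbroken run) or cumulative (sum of runs). It can be measured from first to last value, or with each value carried to the next visit. That gives four readings.

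**Worked example.** Assume 4-weekly values: 0.46 at Weeks 24, 28, 32, 36 and 40; 0.60 at Weeks 44, 48, 52, 56 and 60; 0.85 at Week 64; no other value below 0.8.

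| Time | First to last | Carried forward |
|---|---|---|
| Below 0.5 | 40 − 24 = 16 weeks | 44 − 24 = 20 weeks |
| 0.5 to below 0.8 | 60 − 44 = 16 weeks | 64 − 44 = 20 weeks |
| Below 0.8 | 60 − 24 = 36 weeks | 64 − 24 = 40 weeks |

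Each band is one unbroken run, so consecutive and cumulative time agree. Neither band reaches 24 weeks, so groups 1 and 2 fail. Time below 0.8 exceeds 24 weeks, so group 3 is barred. Values fall below the LLN, so group 4 fails. The subject has no group under any of the four readings.

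**Effect of which values are used.** Keep only the scheduled visits for the same subject and let the recovered value of 0.85 stand at Week 72: 0.46, 0.46, 0.60, 0.60, 0.85 at Weeks 24, 36, 48, 60, 72. Time below 0.5 is 36 − 24 = 12 weeks first to last, and the subject is unclassified. Carried forward it is 48 − 24 = 24 weeks, and the subject is in group 1, the most severe.

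**Enumeration.** Take the 10 scheduled post-baseline CBC visits (Weeks 4, 8, 12, 24, 36, 48, 60, 72, 84, 96) and three levels at each (below 0.5; 0.5 to below 0.8; 0.8 or above). That gives 3¹⁰ = 59,049 patterns. Those fitting no group:

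| Reading | First to last | Carried forward |
|---|---|---|
| Consecutive | 24,624 | 10,962 |
| Cumulative | 25,632 | 1,134 |

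No pattern falls in two groups. The groups are therefore mutually exclusive but not exhaustive on any reading. These are counts of possible patterns, not probabilities.

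**Illustrative size.** A simulation of 20,000 subjects in each of 27 scenarios was scaled to the SAP's 180 evaluable subjects.

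- From the documents: a mean fall of 30% (Protocol 5.3.2) and 24% with at least one value below the LLN by Week 48 (SAP 4). The between-subject spread of the fall was tuned to the 24%.
- Assumed: median baseline ALC 1.7 to 2.1 with SD(log) 0.28 and entry above 0.91; fall complete at Week 24 or 48, then a plateau; within-subject CV 10 to 20%; serial correlation 0 or 0.5.

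Unclassified subjects per 180:

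- consecutive: 0 to 3.4 (0 to 2.5 with scheduled values only);
- cumulative, first to last: 0 to 2.2;
- cumulative, carried forward: at most about 0.2.

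In the 8 of 27 scenarios that also give 14 to 18% with two or more values below the LLN (the SAP's figure is 16%), the maximum is 1.3. Group 1 itself holds 0 to about 6 subjects in the simulation.

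**The case against.** **The parentheses already form a hierarchy.** Group 3's exclusion can be read as shorthand for groups 1 and 2 together, so the authors evidently meant nested groups. That is probably true of the intention. But the written bounds do not nest, and the shorthand reading puts a subject with 24 weeks or more below 0.8 into group 3, against that group's own exclusion.

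**The example needs 4-weekly values to continue after the count rises to 0.60.** Protocol 11.3.2 returns subjects between 500/mm³ and the LLN to the Section 4 schedule. If values then come at Weeks 44, 48, 60 and 72, carried-forward time in the middle band is 72 − 44 = 28 weeks, which is group 2. This stands as far as it goes. First to last, though, the figures are still 16, 16 and 36 weeks and the subject is unclassified. The 4-weekly rule (SAP 2.1; Protocol Table 1, footnote 8) states no end when the count rises above 500. The enumeration uses scheduled visits only and still finds gaps on every reading.

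**The size is small and rests on assumptions.** This stands. The best-calibrated scenarios give at most 1.3 of 180.

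**The tables are descriptive, and the infection link rests on a label.** Both are true. Subgroup totals that fail to add up would also reveal the omission, but only after the data are in hand.

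**Conclusion.** The point holds. Followed literally, SAP 5.3.1 leaves some subjects with prolonged lymphopenia in no group, whichever duration reading is used. The unstated duration rule can separately move a subject between unclassified and group 1. The expected number is small: about 0 to 1 of 180 in the scenarios that match both SAP percentages, and up to 3.4 in the wider set, all conditional on the assumed population. It matters because the severe groups are small, so one or two subjects omitted or misplaced can change a group's infection percentage. The primary estimates, the MMRM, overall summaries, other ALC splits, overall AE tables, listings and the PML listing are unaffected. This should be fixed, but it does not threaten the study's main results.

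**What to change.** In SAP 5.3.1, define group 2 as ALC below 0.8 × 10⁹/L for at least 24 weeks and not meeting group 1. Time below 0.5 is also time below 0.8, and 0.8 lies below the LLN of 0.91. Groups 1 to 4 are then exclusive and exhaustive: in the enumeration every pattern falls in exactly one group under all four readings.

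Also state whether duration is consecutive or cumulative, how time between visits is counted, and whether all ALC values or only scheduled ones are used. In SAP 5.4.1, cite 5.3.1 so that the infection tables use the same rule.

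The alternative, defining group 3 as any value below the LLN and not in group 1 or 2, is equally exhaustive. It would, however, place these subjects in the mildest lymphopenic group.

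The recommended change has one drawback: group 2 then mixes subjects with some values below 0.5 and subjects with none. A footnote giving the number of the former shows this. The cost is a few lines of SAP text and a programming change, with no new data.
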